## FULL PROTOCOL TITLE: Toric Contact Lens Performance Study

We aim to test the hypothesis that  $H_0: \Delta=0$  v.  $H_1: \Delta\neq0$  using a two-sided test with significance level  $\alpha=0.05$ , where  $\Delta$  is the underlying benefit for treatment contact lenses versus spherical contact lenses in this cross-over design. Based on previous studies reported average photopic low contrast visual acuity ranged from 0.3 to 0.4 logMAR with various brands of toric contact lenses and under the same conditions from 0.51 to 0.56 with spherical contact lenses among low-to-moderate astigmatic eyes. An estimated improvement with toric lenses has been reported as  $0.07\pm0.14$  among those with low astigmatism with the magnitude of improvement increasing among those with high levels of astigmatism. It is reasonable to expect a detectable range of 2 letters to half-line of improvement with the treatment contact lenses versus the standard sphere lenses. If we expect a half-line treatment benefit and the within-subject variance of the difference in mean visual acuity between the two periods to be a line (0.1 logMar), then based on pilot-study results, and a required 80% power we need 34 participants overall for each study population (68 total). We will randomize an equal number of subjects to each group (i.e., group A receives treatment 1 in period 1 and treatment 2 in period 2; group B receives treatment 2 in period 1 and treatment 1 in period 2). Depending on the variability, a sample size of 34 in each sampled population allows us to detect a smaller effect size (e.g., high contrast tests) as low as 2.5 letters with a within-subject variability of 0.06 logMar. The visual function testing is novel and has not been used on a population of astigmatic contact lens wearers. So sample size planning cannot be done for these tests. We plan to screen up to 38 participants from the study population to allow for attrition.

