## 6.0 Study Endpoints

The primary study endpoints will compare toric to spherical lenses for:

- Binocular near visual acuity

The secondary study endpoints will compare toric to spherical lenses for:

- Binocular near visual performance
  - Reading speed, errors, etc.
- Contrast
  - Binocular low contrast acuity, contrast sensitivity at near

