1.1.16	Contact Lens Fitting	
Fit subject in the first set of contact lenses based on randomization schedule.
 
 
• The toric lens parameters should be selected based on the manufactures fitting guide.
 
• The powers for the spherical lenses should be the vertexed spherical equivalent.
 
 
After allowing the lens to settle for 10 minutes, assess the fit using slit lamp biomicroscopy.

1.1.17	Contact Lens Over-Refraction	
Perform over-refraction using maximum plus to best visual acuity
 
 
• Perform best sphere and spherocylindrical over-refraction
 

1.1.18	Contact Lens Power Adjustment (if necessary)	Follow the manufactures fitting guide and modify contact lens power, based upon the Contact Lens Over-Refraction, if the subject gains more than 3 letters of acuity with over-

**FULL PROTOCOL TITLE:** Toric Contact Lens Performance Study

		refraction
--	--	------------

Visit 2: Contact Lens Follow Up Lens #1		
Note: Subjects should report wearing their assigned study contact lenses at least 2 hours.		
2.1	Visual Acuity	Perform Distance Snellen acuity OD/OS with the patient's study lens correction.
2.2	Contact Lens Assessment	Assess the fit using slit lamp biomicroscopy.
2.3	Contact Lens Over-Refraction	Perform over-refraction using maximum plus to best visual acuity
2.4	Contact Lens Power Adjustment (if necessary)	Follow the manufacturer's fitting guide and modify contact lens power, based upon the Contact Lens Over-Refraction, if the subject gains more than 3 letters of acuity with over-refraction 

• Perform best sphere and spherical-cylindrical over-refraction

2.5	Slit Lamp Exam with NaFL	Remove the contact lens and instill NaFL then evaluate slit lamp findings using the CCLRU grading scale

Visit 3: Outcome Lens #1		
Note: Subjects should report wearing their assigned study contact lenses at least 2 hours.		
3.1	Visual Acuity	Perform Distance Snellen acuity OD/OS with the patient's study lens correction.
3.2	Questionnaires	Administer the NAVQ to the subject
3.3	High and Low Contrast Near Visual Acuity	Measure logMAR high and low contrast acuity at near OU with high luminance
3.4	Contrast Sensitivity	Perform the contrast sensitivity test on the iPad
3.5	Radner reading test	Perform the Radner reading speed test on the iPad

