Title: Toric Contact Lens Performance Study

NCT number: NCT03546647

Document date:

Protocol: 27 Aug 2018

Statistical Analysis Plan:

The treatment effects on pre-specified outcomes that met the parametric assumptions were analyzed using the Grizzle model (Grizzle, 1965) for the two-period two-treatment crossover trial. First, the data were tested for the presence of a carry-over effect according to the sequence of randomization, that is, sphere or toric, during the first period at the critical level of 0.10. Then, the treatment effect was estimated using a linear mixed model in the presence of period and sequence effects to obtain unbiased effect sizes. For pre-specified outcomes that did not conform to non-parametric testing, Koch's approach using the Wilcoxon rank sum test was used. Treatment differences and 95% Confidence Intervals were estimated using the Hodges-Lehmann method. In the presence of any carry-over effects, hypothesis tests were conducted on period 1 only. Unadjusted p-values are reported and inferred using a specified critical region after adjusting for multiple testing. Summary measures of means and standard deviations are reported for variables conforming to parametric testing and median, 25th percentile, and 75th percentile were reported otherwise. A one-sample binomial test was used to test the hypothesis that the probability of subject preference to treatment lens and standard lenses are equally likely. The hypothesis that $H0: \Delta=0$ vs. $HH1: \Delta\neq0$ using a two-sided test with significance level $\alpha=0.05$ was tested, where Δ is the underlying benefit for treatment contact lenses versus spherical contact lenses in this cross-over design. To assess treatment differences in spatial frequency, a repeated measures model was used and tested for the interaction between spatial frequency and lens type. In the presence of a statistically significant interaction, follow-up testing with appropriate Type I error adjustment was used.

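### The SAP's spatial-frequency analysis names only a lens-by-frequency interaction and no lens main effect, so as written it could miss a toric benefit of similar size at every frequency

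*SAP*

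**What the plan says.** Protocol section 6.0 lists, among the secondary endpoints comparing toric with spherical lenses, "Binocular low contrast acuity, contrast sensitivity at near". Section 7.0 has the measurement taken at both outcome visits (3 and 5) with the instruction "Perform the contrast sensitivity test on the iPad". Neither section gives the spatial frequencies tested or a summary score across them.

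The SAP has two statements that bear on this endpoint.

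- **General rule.** "The treatment effects on pre-specified outcomes that met the parametric assumptions were analyzed using the Grizzle model", and then "the treatment effect was estimated using a linear mixed model in the presence of period and sequence effects". A rank-based alternative is given for outcomes that do not suit parametric testing.
- **Spatial-frequency rule.** To assess treatment differences in spatial frequency, "a repeated measures model was used and tested for the interaction between spatial frequency and lens type". The next sentence reads: "In the presence of a statistically significant interaction, follow-up testing with appropriate Type I error adjustment was used".

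The SAP does not say how the two rules relate, and the spatial-frequency sentence does not mention contrast sensitivity by name.

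**The concern.** The purpose that the SAP gives for the spatial-frequency model is to assess treatment differences, but the one test it names does not do that. A lens-by-frequency interaction tests whether the toric-minus-sphere difference is the same at all frequencies. It is silent on whether that common difference is zero. If toric lenses raise contrast sensitivity by about the same amount throughout, the interaction null is true, the stated trigger for follow-up is usually not met, and the SAP gives no next step for that model.

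At stake is the reading of one secondary endpoint. An analyst following the spatial-frequency text alone could report no lens finding in data that show a clear average benefit. An analyst who falls back on the general rule must first choose how to reduce several frequencies to one value per subject per period, and the documents leave that choice open.

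**Working it through.** **The plan's own figure.** Protocol section 4.0 asks for 34 subjects for a half-line (0.05 logMAR) benefit, 80% power and two-sided α = 0.05, with the "within-subject variance of the difference in mean visual acuity between the two periods to be a line (0.1 logMar". Reading 0.1 as the SD of the paired difference:

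- normal approximation: (1.960 + 0.842)² × (0.10/0.05)² = 31.4, so 32;
- paired t-test (noncentral t): power 0.795 at n = 33 and 0.808 at n = 34.

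The 34 reproduces. It concerns visual acuity; the documents give no sample-size basis for contrast sensitivity by frequency. It is used below only as the number of subjects.

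**Inputs for the check.** From the documents: n = 34, two-sided α = 0.05. Assumed, because the documents give no value: K = 4, 5 or 6 frequencies; per-frequency paired differences with SD 1 and common correlation ρ = 0.2, 0.5 or 0.8; a toric benefit averaging 0.5 SD; no period effect.

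**Interaction test.** With benefit d_k at frequency k and mean benefit d̄, the F test has K − 1 and (K − 1)(n − 1) degrees of freedom and noncentrality

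λ = n × Σ(d_k − d̄)² / (1 − ρ).

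Only departures from the mean benefit enter λ. If every d_k is equal, λ = 0 and the test rejects at rate α, however large the benefit. This follows from the definition of the test and needs none of the assumed values.

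**Lens main effect.** The frequency-averaged difference has variance (1 + (K − 1)ρ)/K, so the paired t-test has noncentrality

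d̄ × √n / √[(1 + (K − 1)ρ)/K].

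- K = 6, ρ = 0.2: variance (1 + 1.0)/6 = 0.333; 0.5 × 5.831/0.577 = 5.05; power 0.998.
- K = 6, ρ = 0.8: variance (1 + 4.0)/6 = 0.833; 0.5 × 5.831/0.913 = 3.19; power 0.873.

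**Simulation, uniform benefit of 0.5 SD** (5,000 trials per setting):

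| K | ρ | Interaction rejects | Lens main effect rejects |
|---|---|---|---|
| 4 | 0.2 | 0.057 | 0.992 |
| 4 | 0.5 | 0.053 | 0.952 |
| 4 | 0.8 | 0.053 | 0.875 |
| 5 | 0.2 | 0.042 | 0.998 |
| 5 | 0.5 | 0.052 | 0.955 |
| 5 | 0.8 | 0.048 | 0.871 |
| 6 | 0.2 | 0.047 | 0.998 |
| 6 | 0.5 | 0.053 | 0.962 |
| 6 | 0.8 | 0.051 | 0.867 |

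**Non-uniform benefit, same average.**

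- Strongly graded, 0 to 1 SD in equal steps. At K = 4, ρ = 0.2: Σ(d_k − d̄)² = 0.556, λ = 34 × 0.556/0.8 = 23.6, power 0.988. Simulated rejection over all settings is 0.989 to 1.000.
- Mildly graded, 0.4 to 0.6 SD in equal steps, from the noncentral F:
  - K = 6, ρ = 0.2: Σ = 0.028, λ = 34 × 0.028/0.8 = 1.19, power 0.107;
  - K = 6, ρ = 0.8: λ = 34 × 0.028/0.2 = 4.76, power 0.335.

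The interaction therefore responds to the shape of the benefit across frequencies. The main effect responds to its average size, which is what section 6.0 asks about.

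**The case against.** The strongest reply is that the general rule already covers the endpoint. Near contrast sensitivity is listed in section 6.0, so it is a pre-specified outcome. The SAP analyses such outcomes with the crossover model and states a two-sided test of zero lens benefit. On that reading the spatial-frequency sentence is an added analysis of where the lenses differ. The interaction is then the right test, and making per-frequency comparisons depend on it is ordinary practice.

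Much of this stands. A reader might infer that contrast sensitivity is tested only through the interaction, or that a uniform benefit would go untested in the trial. The documents do not support either inference: the general rule may apply, and nothing in the SAP forbids reporting a lens effect when the interaction is not significant. A reader might also infer that the spatial-frequency model leaves out period and sequence. That is an argument from silence, since the sentence lists no model terms apart from the tested one. The link from spatial frequency to contrast sensitivity is itself an inference, though no other listed endpoint fits as naturally.

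What the reply does not settle is how the general rule would be applied. The two-period analysis needs one value per subject per period, and no summary across frequencies is defined. The SAP also introduces the spatial-frequency model as its way to assess treatment differences, not as a supplement to an overall test.

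The size of the loss also depends on the pattern. It is confined to uniform or nearly uniform benefits, and it disappears if a contrast sensitivity score does go through the general model.

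**Conclusion.** The point holds as a gap in specification with a real consequence. Within the spatial-frequency model the only named test does not answer the toric-versus-sphere question. No lens main effect and no step after a non-significant interaction are given, and it is unclear whether or how the general rule fills the gap. For a benefit equal at all frequencies, the stated trigger is met in about 5% of trials. A lens main-effect test would reject in about 87% to 99.8%. The 5% follows from the definition of the test. The 87% to 99.8% rests on the assumed 0.5 SD benefit, 4 to 6 frequencies and correlation 0.2 to 0.8, with n = 34.

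The documents do not show that a secondary endpoint is left without any test, and the primary near visual acuity comparison is unaffected. The change should still be made, because the endpoint's test is otherwise open to choice after the data are seen and the correction costs very little.

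**What to change.** Add to the SAP that, in the same repeated-measures model with period and sequence included, the lens main effect averaged over spatial frequencies is the test of the near contrast sensitivity endpoint. Report it with its 95% confidence interval whatever the interaction shows, and count it in the multiplicity-adjusted secondary family. Use the lens-by-frequency interaction and the adjusted per-frequency comparisons to describe where any benefit lies. Name contrast sensitivity in that sentence and list the frequencies.

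If a summary score was in fact analysed under the general crossover rule, define the score and say so instead. The SAP is written in the past tense, so if the results were already known, label the addition as a clarification made afterwards.

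The cost is one sentence, one contrast from a model already being fitted, and at most one more test in the secondary family. No new data are needed.
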